### 6.3 Per Protocol Set

The per-protocol set of subjects defines a subset of the subjects in the Full Analysis Set who also meet the following criteria:

- Received correct treatment for group to which they were randomized
  Were implanted with two MicroLeads
  Reported coverage of in the region of postoperative
- pain during the primary endpoint period (Weeks 5-8) (Group #1 only)

  Not missing more than of average pain intensity (BPI-5) scores in the diaries during
- the primary endpoint period (i.e., Weeks 5-8 of home trial)

  Continued study eligibility throughout treatment period (Weeks 1-8)

Page 12 of 19

### 6.4 Safety Population

The Safety set is based on the Full Analysis Set with the following modifications:

- Subjects will be assessed with an As Treated analysis, with therapeutic group determined by the treatment they actually received.
- Any subjects for whom lead placement is attempted will be included, even if no leads are implanted
- Any subjects for whom treatment is not attempted (*i.e.* no attempted lead placement occurs) will be excluded.

# 6.5 Exploratory Analysis Population – partial and revision knee replacements

### 7.0 Subject Disposition and Baseline Information

## 7.1 Subject Disposition

Study completion and withdrawal details, inclusion and exclusion criteria, randomization, and population assignment will be listed.

Table 1. Subject Disposition Categories

Table 1. Subject Disposition Categories		
Disposition Category	Description	
Screened Potential	All potential subjects who are screened for study participation	
Subjects	will be listed on a screening log. Those potential subjects who	
	are excluded will be listed along with the reason for	
	exclusion. Screened potential subjects include those	
	individuals that were screened from record searches.	
Consented	Any subject who signs an Informed Consent.	
Screen Failures	Any subject who signs an informed consent but does not	
	proceed with randomization will be dispositioned as a screen	
	failure. These subjects will not be counted against allowable	
	site IRB subject totals.	
Randomized	Subjects who sign a consent form, meet all eligibility criteria	
	(including a completed baseline diary), and are assigned to a	
	Group will be considered "randomized" in the study. Any	
	subject who has a lead replaced will still only be counted once	
	against total study enrollment.	

[figure not shown]
Disposition Category	Description
Withdrawn	Subjects who voluntarily withdraw their study participation
	after being randomized will be categorized as withdrawn.
Lost to Follow-Up	After documented attempts at contacting the individual,
	subjects who are unreachable or unresponsive to requests for
Terminated	study visits will be categorized as lost to follow-up.
Terminated	Subjects who are prematurely terminated from the study by
	the Investigator are categorized as terminated. A Study Exit
Completed	Form will capture the reason for study termination.  Subjects who receive one or more leads and complete all
Completed	applicable follow-up visits are categorized as completed.
	applicable follow-up visits are categorized as completed.
	Group #2 subjects that complete Visit 11 will be considered
	Completed. Group #2 subjects may choose to be discharged
	from the study after Visit 11, or cross over to receive
	stimulation. Subjects may be designated Withdrawn, Lost to
	Follow-Up, or Terminated during the crossover treatment or
	crossover follow-up period without impacting their
	Completed disposition in the placebo period.

[figure not shown]
### 7.2 Baseline and Demographic Characteristics

[figure not shown]
Demographic and baseline disease characteristic data will be listed and summarized for each group using descriptive statistics for continuous variables and tabulated for categorical variables.

[figure not shown]
# 8.0 Additional Data Analysis

[figure not shown]
# 8.2 Handling Missing Data

### 9.0 Safety Analysis

All safety data will be analyzed using the Safety Analysis Set. Adverse device effects (ADEs) will be documented, reported, and categorized

### 9.1 Adverse Device Effects

Adverse device effects (ADEs) will be reported and an overall summary of the number and percentage of subjects with at least one ADE, serious ADE, unanticipated ADE, or ADE leading to death will be presented by treatment group.

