### **Protocol Synopsis**

Title	Treatment of Post-Operative Pain Following Orthopedic Surgery with SPRINT® Peripheral Nerve Stimulation (PNS) System in a Randomized, Double-Blinded, Placebo-Controlled Trial
Device (510k Cleared)	The SPRINT® Peripheral Nerve Stimulation (PNS) System
Study Design	Randomized, Double-Blinded, Placebo-Controlled, Multicenter Post Market Study
Primary Study Objective	The study objective is to gather data on the use of the PNS therapy for the treatment of postoperative pain following orthopedic surgery. The study will compare the responses of two groups.
Study Plan	Individuals must have persistent, average pain score of ≥ out of 10 following surgery to qualify Individuals who have undergone primary, unilateral or bilateral total knee replacement (TKR)/revision (PKR) and report unilateral postoperative pain (≥ on an 11-point numerical rating scale on the Brief Pain Inventory Short Form (BPI-SF Question #5)) will be considered for enrollment into the study. After informed consent is obtained, potential subjects will be evaluated for general eligibility. The individuals who satisfy the preliminary criteria will be asked to complete an assessment of baseline pain to determine if their postoperative pain is persistent.  Percutaneous leads will be placed to target the nerves
	innervating the region of pain  Qualifying subjects will be randomized to either Group #1 (Treatment) or Group #2 (Control). In all subjects, leads will be placed  All subjects will be instructed to use the SPRINT Stimulator  during the 8-week treatment period. In Group #1, the system will deliver active electrical stimulation, while in Group #2, the system will deliver sham (placebo) stimulation during the 8-week treatment period.  After lead removal, Group #1 subjects will be followed for 12 months from the start of treatment (SOT).
	Group #2 will be given the option of crossing over Following the completion of a follow-up visit  Group #2 subjects will be given the option of crossing over to receive active stimulation. If subjects do not choose to receive active stimulation, they will be discharged from the study. If subjects choose to receive active stimulation, leads will again be placed

Sites (N)	Up to 15 sites
Subjects (N)	Up to subjects will be randomized
Inclusion Criteria	At least 21 years old

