### 4.4.1.2 Primary Safety Endpoint

[figure not shown]
The primary safety endpoint is the occurrence and type of study-related adverse events, also known as adverse device effects (ADEs). All ADEs that occur during the study will be documented and analyzed.

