### 5.2.9 Telephone Follow-up

All subjects will receive a Telephone Follow-up 24 - 48 hours after lead placement to query for any adverse device effects (ADE). All ADEs will be followed until resolution.

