#### 3.1 Randomization

Qualifying individuals will be randomized to either Group #1 (Treatment) or Group #2 (Control) using permuted-block randomization. Eligibility and the schedule and procedure for randomization are detailed in the study protocol (0150-CSP-000).

Subjects included in the primary endpoint analysis (subjects who have undergone a primary TKR) will be randomized separately from subjects in the exploratory analysis group (subjects who have undergone a PKR or secondary/revision TKR) to maintain an appropriate distribution for the primary endpoint analysis. Individuals will be blinded to their randomization assignment until the close of Visit 11 (3-mo after start of therapy).

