### 5.2.2 Long-term Durability of Pain Relief at 3, 6, 9, and 12 months after SOT

The analysis of the durability of the treatment effect on average pain intensity will be conducted at 3, 6, 9, and 12 months after the start of therapy by comparing the proportion of subjects who successfully achieve  $\geq 50\%$  reduction from baseline in Group #1 at each time point compared to 3 months after the start of therapy (the longest follow-up before crossover) in Group #2 using a Fisher's exact test. The pain intensity scores will be determined for each subject by applying the same method used for the primary endpoint: taking the mean of the daily average pain intensity (BPI-SF Question #5) reported in the 7-day diary at baseline compared to the mean score reported in the follow-up diary (*i.e.*, 3, 6, 9, or 12 months after SOT for Group #1; compared to 3 months after SOT in Group #2). To be considered a success, subjects must have  $\geq 50\%$  reduction in pain. The null hypothesis is that there is no difference in the proportions of success between the two treatment groups, versus the alternative hypothesis, that the proportions of success differ from one another. Testing will be conducted at the 0.05 level of significance.

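### The by-group ADE percentages in SAP 9.1 have no stated common observation window, although follow-up runs to about 3, 12 or 15 months depending on group and crossover choice

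*SAP*

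**What the plan says.** Protocol 4.4.1.2 makes the occurrence and type of adverse device effects (ADEs) the primary safety endpoint and adds: "All ADEs that occur during the study will be documented and analyzed". It gives no cut-off date. SAP 9.1 then plans an overall summary of the "number and percentage of subjects with at least one ADE", with similar rows for serious, unanticipated and fatal ADEs, shown by treatment group. The section mentions no analysis period, person-time or split at crossover.

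Follow-up differs by group and by choice:

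- **Group #1.** The synopsis runs follow-up to month 12 from SOT. Protocol 5.19, Table 4 lists calls at 6, 9 and 12 months.
- **Group #2, declining crossover.** The synopsis says: "If subjects do not choose to receive active stimulation, they will be discharged from the study". SAP 7.1, Table 1 places this choice after Visit 11, and SAP 3.1 puts Visit 11 at 3 months.
- **Group #2, crossing over.** Leads are placed again (Protocol 5.13), and calls continue to 12 months after the start of crossover treatment (Protocol 5.17).

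Protocol 5.10 has the leads removed in both groups at week 8. SAP 6.4 assigns subjects in the safety set by treatment received. Its public text does not say how to handle someone who received sham and then active stimulation.

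**The concern.** The share of subjects who ever had an event rises, or at least cannot fall, as observation lengthens. If two columns rest on different observation times, they can differ when the underlying risk is the same, or agree when it is not. This table is the only by-group ADE summary in the public SAP text, so readers will use it to judge whether active stimulation carries more device-related harm than sham.

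The SAP already deals with this asymmetry elsewhere. For durability of pain relief, Group #1's later time points are set against "3 months after the start of therapy (the longest follow-up before crossover) in Group #2", and SAP 5.2.3, 5.2.4, 5.2.6 and 5.2.7 repeat the idea. SAP 7.1, Table 1 also keeps crossover-period withdrawals from altering a subject's disposition in the placebo period. The safety section has no matching rule.

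**Working it through.** **1. Reproduce the plan's own timeline.** Protocol 4.2.3 gives about 13 months' participation for Group #1 and about 16 for Group #2 with crossover.

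- Time before SOT, from Group #1: 13 − 12 = about 1 month.
- Group #2 with crossover: 1 + 3 (to Visit 11) + 12 (after start of crossover treatment) = 16 months, which matches.

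**2. Observation after SOT.**

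| Subjects | Months from SOT | Lead placement visits |
|---|---|---|
| Group #1 | 12 | Visit 2 |
| Group #2, declines crossover | about 3 | Visit 2 |
| Group #2, crosses over | 3 + 12 = about 15 | Visit 2 and Visit C1 |

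Group #1 against decliners is 12/3 = 4 to 1. After lead removal at day 56 it is 365 − 56 = 309 days against about 91 − 56 = 35 days.

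**3. What this can do to the percentages.** The documents give no ADE rates and no crossover fraction, so everything in this step is assumed and shows direction only. Let q be the risk of at least one ADE by Visit 11, equal in both groups. Let h be the monthly hazard of a first ADE over the next 9 months, and c the fraction of Group #2 who cross over.

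*Group #1:* P1 = 1 − (1 − q) × exp(−9h).

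*(a) Only sham-period events count under Group #2.* The Group #2 percentage stays at q. With q = 30%:

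| h per month | Group #1 | Group #2 | Difference (points) |
|---|---|---|---|
| 0 | 30.0% | 30.0% | 0 |
| 0.002 | 31.2% | 30.0% | 1.2 |
| 0.005 | 33.1% | 30.0% | 3.1 |
| 0.01 | 36.0% | 30.0% | 6.0 |
| 0.02 | 41.5% | 30.0% | 11.5 |

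Over the same values of h, the difference runs from 0 to 14.8 points for q = 10% and from 0 to 8.2 points for q = 50%.

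*(b) Crossover-period events stay under Group #2.* Assume the second placement carries risk q again. A crossover subject's cumulative risk is Px = 1 − (1 − q)² × exp(−9h), and the Group #2 percentage is (1 − c) × q + c × Px.

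- q = 30%, h = 0, c = 0.5: Px = 1 − 0.49 = 51.0%, so Group #2 is 0.5 × 30.0 + 0.5 × 51.0 = 40.5%, against 30.0% in Group #1.
- q = 30%, h = 0.01, c = 0.5: 42.6% against 36.0%.
- With q = 30% and h = 0.01, Px is 55.2%. The columns are equal when c = (36.0 − 30.0)/(55.2 − 30.0) = about 0.24. Below that fraction Group #1 looks worse, and above it Group #2 does.

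The true risk from one placement is equal in both groups in every row. The sign and size of the difference come only from h, c and the counting rule.

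**4. With a common window.** If both columns cover SOT through Visit 11, each shows q and the artificial difference is 0 points, whatever h and c are.

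**The case against.** **The table is descriptive.** SAP 9.1 names no test, and the hypotheses in SAP 4.0 include none on safety. This stands: the issue is how two adjacent columns will be read, not an invalid test. Readers will still compare them.

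**The rule may be in withheld text.** In the public version, the sentence in SAP 9.0 breaks off after saying that ADEs will be categorised. The bodies of Protocol 5.11 and 5.12 and the Appendix A schedule are not shown, so what is asked about ADEs at the 6, 9 and 12 month calls cannot be seen. This also stands, and the request must be to state or confirm the window. The sentence in SAP 9.1 itself is complete, however, and followed as written it sets no window.

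**Late ADEs may be rare.** Leads are out at week 8 in both groups, about 35 days before Visit 11, and Protocol 10.0 captures only events that are study-related or of undeterminable relationship. This stands, and zero belongs in the range.

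**Follow-up of open ADEs.** A reader might infer that discharging a sham subject at Visit 11 contradicts Protocol 5.2.9, which says: "All ADEs will be followed until resolution". The documents do not support that. Protocol 10.0 also has ADEs followed to resolution without a group exception, and nothing says that discharge ends follow-up of an open ADE.

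**Conclusion.** The point holds as a like-for-like problem in the summary of the primary safety endpoint. As SAP 9.1 publicly reads, about 12 months of observation in Group #1 sits beside a Group #2 mixture of about 3 and about 15 months, the latter with a second, active placement.

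A reader might infer that the table is biased against active stimulation. That follows only if sham-period events alone count under Group #2, and the documents do not fix that rule. If crossover-period ADEs are counted under Group #2, the difference can reverse.

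A reader might also want one figure for the distortion. None can be derived: the percentages in the working rest on assumed rates and an assumed crossover fraction, and the effect may be near zero. The durations themselves come from the documents and agree with the stated participation times. The conclusion also assumes that no withheld text sets a window. On that footing this is an inexpensive improvement, not a serious flaw.

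**What to change.** Unless withheld text already does so, add to SAP 9.1:

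- The by-group ADE summary covers SOT (lead placement) through Visit 11 in both groups.
- Group #1 ADEs with onset after Visit 11 are reported in a separate table without a sham comparator.
- Group #2 crossover-period ADEs are reported in a further separate table, also without a sham comparator.

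Separately, ask the sponsor to confirm that the discharge wording in the synopsis and Protocol 5.0 is meant to be consistent with the ADE follow-up wording in Protocol 5.2.9 and 10.0.

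The cost is a few lines of SAP text and sorting captured events by onset date. No visit or assessment is added. The downside is that late events leave the side-by-side table, but they remain fully reported.
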